4. FINANCIAL INTERESTS: Indicate below if any investigators or any members of their immediate families have any relationships, commitments, or activities with the sponsor of this research that might present or appear to present a conflict of interest with regard to the outcome of the research. (If a financial conflict of interest exists, please submit the UIUC approved conflict management plan. If you have questions about conflict of interest contact the Office of the Vice Chancellor for Research at [contact].)

Ownership, equity or stock options
 Has been disclosed to the UIUC campus **OR** has not been disclosed to the UIUC campus

Personal compensation such as royalties, consulting fees etc.
 Has been disclosed to the UIUC campus **OR** has not been disclosed to the UIUC campus

Intellectual property such as patents, trademarks, copyright, licensing, etc.
 Has been disclosed to the UIUC campus **OR** has not been disclosed to the UIUC campus

Other conflict of interest:
 Has been disclosed to the UIUC campus **OR** has not been disclosed to the UIUC campus

No conflicts exist

5. SUMMARIZE THE RESEARCH. In LAY LANGUAGE, summarize the objectives and significance of the research.

Rates of alcohol and illicit drug use (AIDU) among residents of distressed communities with concentrations of African Americans (DCAA- i.e., localities with high rates of poverty and crime) are similar to the general population. Yet AIDU has significantly higher consequences for residents in DCAs (e.g., higher incarceration and HIV/HCV infection rates), who also have considerably less access to effective treatment of substance use disorders. This project will continue to develop and test *Community Wise*, an innovative multi-level intervention created in partnership with service providers, residents of DCAs and individuals with histories of substance use disorders and incarceration, to reduce health inequalities related to AIDU. We used community-based participatory research (CBPR) to develop and pilot test *Community Wise*, achieving 75% intervention completion rates, despite great participant challenges (such as homelessness, AIDU, and poverty). Note that substance use disorder intervention completion rates in the literature are much lower among populations with fewer challenges (often 30 to 40%). We believe that this success is due to the CBPR model used to develop an intervention that is relevant to participants' needs.

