Determine if psychotic symptoms are due to drug use

Do these psychological problems happen only when or after you have been using alcohol or other drugs?
 
Do these psychological problems happen even when you have not been using alcohol or other drugs?
 
DO NOT ASK THIS, USE YOUR JUDGMENT TO ANSWER: Are psychotic symptoms drug induced?
 
Does participant have psychotic symptoms that are likely to intervene with participation in Community Wise?
	 Yes  No

Clinician notes to support their recommendation.
	

(Notify participant that if they seek treatment for these symptoms they can become eligible in the future.)

Timeline Follow Back Alcohol Use Questions

Number of days on which alcohol was used in the past 30 days.
	<hr/>

Average number of drinks per drinking day in past 30 days. (NOTE: MUST WRITE 1 DECIMAL PLACE, e.g. 0.0). To get this number, add the total number of drinks in the month, then divide it by the number of drinking days.
	<hr/>

Number of heavy drinking days. (Heavy Drinking = 4 or more drinks in one occasion) _____

Timeline Follow Back Drug use questions

Number of days on which heroin was used in the past 30 days. _____

How much heroin do you typically use in a day? _____

Number of days on which cocaine was used in the past 30 days. _____

How much cocaine do you typically use on a day? _____

Number of days in which cannabis was used in the past 30 days. _____

How much cannabis do you typically use on a day. _____

Number of days on which prescription opiates was used in the past 30 days. _____

How much prescription opiates do you typically use on a day. _____

Number of days on which prescription downers (Benzos, Barbiturates) was used in the past 30 days. _____

How much prescription downers do you typically use on a day. _____

Number of days on which hallucinogens was used in the past 30 days? _____

How much hallucinogens do you typically use on a day? _____

Number of days on which synthetic marijuana was used in the past 30 days? _____

How much synthetic marijuana do you typically use on a day? _____

Number of days in which other drug was used in the past 30 days _____

How much other drugs do you typically use a day? _____

Specify other drug _____

Did the participant meet the weekly use in the past month threshold? (4 or more days using any drug or 4 or more days of binge drinking) _____

Yes
 No

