Please select the choices that best represents your level of agreement that each statement describes who you are today. There is no right or wrong answer.

	Agree	Somewhat Agree	Slightly Agree	Slightly Disagree	Somewhat Disagree	Disagree
I challenge the oppressive culture under which we live (messages, images, and language) by learning about the issues that affect my community						
Oppressed individuals can overcome barriers that keep us from getting ahead by working together						
People of color can combat oppression by re-defining family values to reflect their own history and standards						
Individuals who adopt distorted cultural messages about themselves without realizing it, become participants in their own oppression						
Working as a community on civic engagement can change our perceptions of ourselves and of others						
In my community, I can find resources (e.g. knowledge, support, partners) to help me work against the biases and "isms" that try to hold us back						
My own experiences are valuable resources that I can share with members of my community so that together we can work against oppression						
I feel disconnected from others						
I am able to listen to what other people have to say						

I attend meetings where we discuss issues about my community						
I work with my community to hold my government representatives accountable						

TLFB

Use the Calendar Handout to answer the following questions (note these questions refer to last month).

Instructions: Please look at the calendar over the past month and note all of the special occasion days you can recall (e.g. someone's birthday, important event occurred, etc). Then go back to the calendar and try to rebuild how much alcohol/drug you used every day during the past 3 months. You will write everyday how many drinks/hits you took each day. Refer to the alcohol handout to make sure you are recording the amounts properly. Then answer the following questions:

In the past month HOW MANY days did you drink alcohol last month? _____

On the days you drank, how many standard drinks (6 ounces) did you have per day? _____

In the past month HOW MANY days did you use Heroin last month? _____

On the days you used Heroin, how much did you use per day? _____

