In the past month HOW MANY days did you use Cocaine last month? _____

On the days you used Cocaine, how much did you use per day? _____

In the past month HOW MANY days did you use Cannabis last month? _____

On the days you used Cannabis, how much did you use per day? _____

In the past month HOW MANY days did you use Opiates last month? _____

On the days you used Opiates, how much did you use per day? _____

In the past month HOW MANY days did you use Downers last month? _____

On the days you used downers, how much did you use per day? _____

In the past month HOW MANY days did you use Hallucinogens last month? _____

On the days you used Hallucinogens, how much did you use per day? _____

In the past month HOW MANY days did you use Synthetic Marijuana last month? _____

On the days you used Synthetic Marijuana, how much did you use per day?

In the past month HOW MANY days did you use other drugs last month?

On the days you used other drugs, what are the drugs you used and how much did you use per day?

GAIN**In the past 30 days did you...**

	Yes	No
c try to hide that you were using alcohol or other drugs?		
d your parents, family, partner, co-workers, classmates or friends complained about your alcohol or other drug use?		
e used alcohol or other drugs weekly or more often?		
f your alcohol or other drug use caused you to feel depressed, nervous, suspicious, uninterested in things, reduced your sexual desire or caused other psychological problem?		
g your alcohol or other drug use caused you to have numbness, tingling, shakes, blackouts, hepatitis, TB, sexually transmitted disease, or any other health problems?		
h keep using alcohol or other drugs even though you knew it was keeping you from meeting your responsibilities at work, school, or home?		
j repeatedly used alcohol or other drugs when it made the situation unsafe or dangerous for you, such as when you were driving a car, using a machine, or when you might have been forced into sex or hurt?		
k your alcohol or other drug use caused you to have repeated problems with the law?		
m		

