- Structured living situation, e.g., recovery house, group home, halfway house
- Homeless shelter
- Homeless, i.e., on the street, in an abandoned building, in a car

Specify the institution

Select all that apply

Did you receive any services for drug and/or alcohol in the past month? Select the types of substance abuse treatment you received. (Check as many as apply)

- For alcohol or drug problems (incl. dual dx)
- For psychological or emotional problems
- For medical problems
- For criminal behavior or legal problems
- For domestic violence
- Outpatient group therapy
- Individual group therapy
- Residential program
- Detox
- 12 steps meetings/ program
- Prescriptions (e.g. methadone, naltrexone, Antabuse, Vivitrol, Suboxone)
- Needle exchange program
- Drop-in center
- Smoking cessation

List the medications you took over the past month and what you used it for.

In the past month, how many days did you attend treatment for emotional or psychological problems?

How many times were you hospitalized in the past month?

How many times did you visit the emergency room in the past month?

How many times did you see a medical doctor in the past month?

Did you receive any HIV treatment in the past month?

In the past month, how many counseling sessions did you attend specifically for prevention of or education about communicable/infectious diseases (e.g. HIV, Hepatitis, STD)?

Did you receive any family related services such as Dfs, parenting classes, family therapy?

How many sessions did you attend where job/education counseling, placement was the main focus in the past month?

- Yes
- No

- Yes
- No

How many sessions did you attend where specific housing services were main focus in the past month?

How many sessions did you attend where financial/benefits issues were main focus in the past month?

How many times did you meet/speak with a probation/parole/pre-trial supervision officer in the past month? (exclude reschedules, cancels, etc.)

How many times did you meet/speak with a public defender or criminal defense lawyer/legal assistant in the past month? (exclude reschedules, cancels, etc.)

Did you receive any other services during past 30 days (e.g. psych testing, food bank, soup kitchen)?

Yes

No

Specify the other services you received.

TSR

Given all the services and treatments and contacts you've had in the past 30 days, how much of all these services dealt with:

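### The TLFB opiate and downer items do not separate medicine taken as prescribed from non-prescribed use, although the outcome is alcohol and illicit drug use

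*Combined protocol and SAP*

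**What the plan says.** - **Construct.** Section 5 (Summarize the Research) opens with "Rates of alcohol and illicit drug use (AIDU". It says that the refined intervention will keep only components that significantly reduce this outcome.
- **Measure.** Section 10, under Measures, names the TLFB as the measure of drug use at baseline and follow-up, alongside a urine screen. Section 15 also lists the TLFB at both times.
- **Baseline items.** The TLFB block of the Baseline Survey asks "In the past month HOW MANY days did you use Opiates last month" and "In the past month HOW MANY days did you use Downers last month". Heroin has its own item. The instruction reads "You will write everyday how many drinks/hits you took each day" and does not mention prescribed medicine.
- **Screening items.** The Clinical Screening Survey asks "Number of days on which prescription opiates was used in the past 30 days" and "Number of days on which prescription downers (Benzos, Barbiturates) was used in the past 30 days". Its weekly-use threshold is "4 or more days using any drug or 4 or more days of binge drinking".
- **Medication data.** The TSR block of the Baseline Survey has a checkbox for "Prescriptions (e.g. methadone, naltrexone, Antabuse, Vivitrol, Suboxone" among services received, and a free-text list of medicines and their purpose. Neither records days.
- **Other services.** Section 10 says that other services will be tracked and controlled for statistically. It names no model or variable.

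**The concern.** The construct is illicit use, but the items ask about drug classes that include medicines prescribed to treat the disorder under study. The screening labels go further: a man who takes a prescribed opioid or benzodiazepine answers them correctly by counting every day he takes it. The only place where the survey addresses prescribed medicine in a use question is the injection item, and there it asks for prescribed medicine to be included. Section 18B has participants work independently on a tablet, so a doubtful reading need not be caught.

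Exposure is plausible. Men are recruited through substance abuse agencies, the site offers substance abuse treatment, and the safety plan in Section 20C provides for referral to detoxification and further treatment. If one factor level led more men into medication treatment, and they reported the medication on these items, a benefit could register as drug-use days. The component could then look weaker in the decision about what to keep. At entry, prescribed days can count toward the any-drug threshold.

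**Working it through.** The plan states no figure that can be reproduced here. The available text gives no alpha, power, effect size or SD, and no formula that turns TLFB days into the outcome. The check is therefore a comparison of wording, followed by an illustration on assumed inputs.

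**1. Wording**

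| Place | Label | As-prescribed exclusion | Day count |
|---|---|---|---|
| Screening TLFB | prescription opiates; prescription downers | none | yes |
| Baseline TLFB | Opiates; Downers (heroin asked separately) | none | yes |
| Follow-up TLFB | form not shown | unknown | unknown |
| TSR checkbox | treatment prescriptions | not applicable | no |
| TSR medication list | free text with purpose | not applicable | no |

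No available text connects the first three rows to the last two. The opiate label also changes between screening and baseline, and the baseline item does not say 'other than heroin'. Heroin days could therefore be entered under both items. That matters only if the items are summed, and no summing rule is given.

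**2. One man (assumed)**

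Suppose any-use days in a 30-day month are max(heroin days, medication days). A man has 12 heroin days at baseline. Later he has 0 heroin days and takes prescribed medication daily.

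- If he enters the medication under opiates: max(0, 30) = 30, a change of 30 − 12 = +18 days.
- If prescribed days are excluded: 0, a change of 0 − 12 = −12 days.
- If he does not regard the medication as an opiate: 0 on either form.

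His separate heroin item falls from 12 to 0 in every case.

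**3. Bias in a two-level factor contrast (assumed)**

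Bias in mean any-use days = d × r × (30 − u). Here d is the difference in medication uptake between the factor levels, r is the share of those men who report it under opiates, and u is their other use days. Medication is taken daily and the u days overlap it.

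| d | r = 0 | r = 0.5, u = 0 | r = 1, u = 0 | r = 1, u = 10 |
|---|---|---|---|---|
| 0 | 0 | 0 | 0 | 0 |
| 2% | 0 | 0.3 | 0.6 | 0.4 |
| 5% | 0 | 0.75 | 1.5 | 1.0 |
| 10% | 0 | 1.5 | 3.0 | 2.0 |

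The bias runs against the level with more medication uptake.

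**4. Scale**

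Section 10 gives 592 men, so a balanced factor has 592 / 2 = 296 per level. With two-sided 0.05 and 80% power assumed, and clustering and dropout ignored, the detectable difference is (1.960 + 0.842) × SD × √(2/296). That is 1.84, 2.30 or 2.76 days for an assumed SD of 8, 10 or 12. Only the 10-point row with full reporting reaches this range.

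**5. Entry**

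Thirty days exceeds the 4-day threshold. But the clinician's eligibility item combines a lifetime or past-year disorder with past-year use or the threshold, and Section 9 requires a disorder on the GAIN-SPS. A man with a lifetime disorder and any past-year drug or alcohol use already meets the item, so the threshold would seldom decide his entry.

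**The case against.** The strongest reply is that misclassification is possible but not shown. The instruction speaks of drinks and hits, which suggests non-medical use. The survey presents methadone and Suboxone as treatment, trained staff administer it, and the calendar handout, which might clarify the point, is not in the available text. The TSR, the urine screen and the past-30-day GAIN problem items give other views of use. The tracking sheet has a column for a filed medication sheet, whose content is not shown.

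Much of this stands, and it rules out several stronger readings:

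- A reader might infer that a man who enters methadone or Suboxone treatment necessarily scores as a maximal illicit user. That needs him to report the medication as an opiate, and a scoring rule that counts those days as illicit. The documents establish neither.
- A reader might infer that factor effects are biased. Nothing shows that uptake differs by factor level. The post-intervention referral in Section 20C is on request and is not tied to any component.
- A reader might infer that men without illicit use are admitted through the threshold alone. The disorder criterion in Section 9 does not support that.

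The reply does not remove the ambiguity. Collecting medication data is not a rule for using them, and the TSR has no day count. Controlling for services would adjust for a post-randomisation variable and leave the day count unchanged. The urine result is described only as added information, with no rule for a positive explained by a prescription.

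**Conclusion.** The point holds as a measurement defect of uncertain size. As worded, the screening and baseline items let prescribed days be recorded as drug-use days, up to 30 a month, and nothing in the available text prevents those days from counting as illicit use.

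The effect on a factor contrast is 0 to 0.6 days per month for a 2-point difference in uptake and 0 to 3.0 days for a 10-point difference. It is zero if uptake is equal. These figures rest on an assumed any-use summary, daily medication and assumed uptake gaps; the documents supply none of these. That the follow-up form has the same wording is also an assumption: the TLFB is listed at follow-up, but the form is not shown.

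**What to change.** 1. On the screening and baseline TLFB, and on the follow-up TLFB if it has the same wording, change the items to *opiates other than heroin, not prescribed to you or not taken as prescribed* and *downers not prescribed to you or not taken as prescribed*. Use the same labels on every form.
2. State in the analysis plan that days of medication taken only as prescribed are not outcome days. Reconcile the wording of the 4-day screening threshold with the illicit-use construct.
3. For completed forms, use the TSR prescription checkbox and medication list to flag affected men, and run a sensitivity analysis that excludes their opiate or downer days. An exact recode is not possible: the TSR has no day count, and some of these men may also misuse the same class.
4. Read urine positives for the same class against the medication list, by a rule fixed in advance.

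The cost is two reworded items and a coding rule that uses data already collected. If the change is made mid-trial, wording will differ between earlier and later waves, and the flag only partly addresses that.

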Procedure The following steps are to be followed in the event of a medical emergency: 1. The responding staff member must call 911 immediately. Staff must disclose to the operator the specific Integrity House location. 2. Integrity House medical staff must be contacted immediately and notified of the situation. 3. Staff trained in and/or certified in first aid may begin attending to the client with appropriate first aid procedures. 4. Attending staff are to provide all relevant information to emergency personnel upon arrival. 5. Clients and staff experiencing medical emergencies are to be transported to the nearest medical facility by ambulance or other medical emergency vehicles. 6. The Program Director must be notified of the medical emergency within two (2) hours. 7. An incident report must be filed as per Policy I-1.14: Incident Reports . 8. If the medical emergency results in death, Policy I-1.31: Death on the Premises or Policy I-1.87: Death off of the Premises is to be followed. 9. A client's emergency contact must be notified of the medical emergency (provided that a signed release allowing disclosure is present in the client's file). 10. A client's referral source must be notified of the medical emergency (provided that a signed release allowing disclosure is present in the client's file). 11. If the medical emergency has the potential to cause an outbreak of a contagious disease the Medical Director, The Director of Nursing, the Chief Executive Officer, and the Chief of Operations must be notified within two (2) hours. If necessary the Medical Director the will report to the New Jersey Department of Health any necessary information regarding any diseases listed in NJAC 8:57 -1.3 Reportable Diseases.	
Medical Director's Signature	 Date 1/22/15

Senior Management Approval		Date	6-30-15
President's Signature		Date	6-30-15
Initial Policy Date: 4/6/1999 Revised: 6/19/2015 PRC: N/A			

INTEGRITY, INC.

Policy and Procedures Form

RECEIVED
MAR 21 2016
INST REVIEW BOARD

Facility/Department: Secaucus	Integrity Policy #: I-1.64
Subject: Emergency Room Referral for Clients	Administrative  Clinical  Human Resources 
Purpose: To provide guidelines for the referral of clients to the emergency room.	
Procedures 
1. If a staff member believes that a client needs to go to the emergency room due to illness or injury, medical staff should be contacted immediately.2. If the medical staff determines that the client needs to be seen in the emergency room the staff in charge must arrange transportation of the client to the emergency room. If the incident is a medical emergency refer to Policy I-1.28: Medical Emergencies. Note: in the case of a medical emergency the client can only be transported to the Emergency Room by emergency personnel.3. The client's emergency contact must be notified by the staff (provided that a signed release is present in the client's file).4. The client's referral source must be notified by staff (provided that a signed release allowing disclosure is in the client's file).5. The staff in charge must file an incident report as per Policy I-1.14 Incident Reports.	
Martin's Place and [name] 
1. If a staff member believes that a client needs to go to the emergency room due to illness or injury the staff in charge must arrange transportation of the client to the emergency room. If the incident is a medical emergency refer to Policy I-1.28: Medical Emergencies. Note: In the case of a medical emergency the client can only be transported to the Emergency Room by emergency personnel.2. The client's emergency contact must be notified by the staff (provided that a signed release is present in the client's file).3. The client's referral source must be notified by staff (provided that a signed release allowing disclosure is in the client's file).4. The staff in charge must file an incident report as per Policy I-1.14 Incident Reports.	
Medical Director's Signature	[name] Date 6/22/15
Senior Management Approval	[name] Date 6-30-15
President's Signature	MM Date 6-30-15
Initial Policy Date: 11/19/1999	
Revised: 6/19/2015	
PRC: 6/27/2011	

Community Wise Referral List

Type of Service	Organization	Address	Address 2	Telephone	Description of Services
AIDS/HIV	AIDS Resource Foundation for Children, Inc.	[name]	Newark, NJ 07102	[contact] (X737 for [name])	Housing, medical support, etc for children and families with AIDS & other serious medical conditions.
